Appendix I Visit windows

Main Cohort, Immediate Vaccination, Visit Windows

Visit Number	Visit Type	Lower Allowable Window	Lower Target Day	Target Day ¹	Upper Target Day	Upper Allowable Window
01.0	Screening	-56	-		-	0
02.0	Enrollment/Randomization ²	-	-	1	-	-
03.0	Vaccination 2	-	-3	29 ³	+7	+14
04.0	Month 2 Follow-up	-	-7	57	+7	+14
05.0	Month 4 Follow-up	-13	-7	113	+14	+56

1. Target dates are relative to Visit 2.0 (Enrollment/Randomization), except for cases described in footnote 3.

2. Completion of post enrollment activities may occur up to approximately 7 days post enrollment (see Section 9.3).

3. In the event that Vaccination 1 occurs on a different day than Visit 2.0 (Enrollment/Randomization), Visit 3.0 target dates are relative to date of Vaccination 1.

Main Cohort, Standard of Care and Vaccine Declined, Visit Windows

Visit Number	Visit Type	Lower Allowable Window	Lower Target Day	Target Day ¹	Upper Target Day	Upper Allowable Window
01.0	Screening	-56	-		-	0
02.0	Enrollment/Randomization ²	-	-	1	-	-
04.0	Month 2 Follow-up	-	-7	57	+7	+14
05.0	Vaccination 1 ³	-13	-7	113	+14	+28
06.0	Vaccination 2 ^{1,3}	-	-3	141	+7	+14

1. Target dates are relative to Visit 2.0 (Enrollment/Randomization), except visit 06.0, which is relative to visit 05.0.

2. Completion of post enrollment activities may occur up to approximately 7 days post enrollment (see Section 9.5).

3. Vaccination visits only apply to participants who have not received COVID-19 vaccine outside the study and for participants in the Vaccine Declined Group who request to be vaccinated.

Case-Ascertained Close Contact (CACC) Cohort and applicable Prospective Close Contact (PCC) participants¹, Visit Windows

Visit Number	Visit Type	Lower Allowable Window	Lower Target Day	Target Day ²	Upper Target Day	Upper Allowable Window
200.0	Enrollment	-	-	1	-	-
201.0	Initial blood specimen collection		-2	3	+1	+4
202.0	Day 29 Follow-up	-	-7	29	+14	+28

1. Applicable to PCC participants when they (or their Main study contact) tests positive for SARS-CoV-2.

2. Target dates are relative to Visit 200.0 (Enrollment).

1. LIST OF ABBREVIATIONS AND ACRONYMS

Term/Abbreviation	Definition
Ab	Antibody
AUC	Area under the curve
CACC	Case-Ascertained Close Contact
CI	Confidence Interval
CONSORT	Consolidated Standards of Reporting Trials
COVID-19	Coronavirus disease 2019
CoVPN	COVID-19 Prevention Network
CRF	Case report form
CT	Cycle threshold
FAS	Full analysis set
FAS-P	Full analysis set with PCR data
GEE	Generalized estimating equations
IPCW	Inverse-probability-of-censoring weighting
ITT	Intention-to-treat
mRNA	Messenger ribonucleic acid
PCC	Prospective Close Contact
PCR	Polymerase chain reaction
RCT	Randomized clinical trial portion of the study
RNA	Ribonucleic acid
RT-PCR	Real time polymerase chain reaction
SARS-CoV-2	Severe acute respiratory syndrome coronavirus 2
SD	Standard deviation
VED	Vaccine efficacy against COVID-19 disease
VEI	Vaccine efficacy against infectiousness
VES	Vaccine efficacy against susceptibility
VL	Viral load

2. INTRODUCTION

This SAP describes the statistical analysis of CoVPN 3006, a partly randomized and controlled study to evaluate the effects of the mRNA-1273 COVID-19 vaccine on SARS-CoV_2 infection and viral load.

The SAP was modified after the study was stopped early in January 2022, to reflect that some study objectives cannot be addressed, and other study objectives require modification of analysis methods.

2.1 General Design Considerations

This is a Multicenter, randomized, controlled, open-label trial augmented by an observational cohort. Participants were enrolled into one of three cohorts with two distinct groups comprising the Main Cohort.

Main Cohort (main study participants)

Up to approximately 18,000 healthy volunteers, aged 18 through 29 years, who will be followed for up to 5 months after enrollment; up to 6,000 randomized to Immediate Vaccination Group, up to 6,000 randomized to Standard of Care Group, and up to 6,000 non-randomized to Vaccine Declined Group.

Prospective Close Contact (PCC) Cohort

Up to approximately 36,000 volunteers who are in frequent close physical proximity with main study participants

Case-Ascertained Close Contact (CACC) Cohort

Expected average approximately 3 contacts per incident case. Actual total number dependent on incidence rate. Up to approximately 2250 volunteers aged 18 years and older who have been in close contact with a SARS-CoV-2 positive case from the Main Cohort

Table 2-1 Schema for the Main Cohort

Group	N	Injection schedule in months			
		0	1	4	5
Randomized Groups					
Immediate Vaccination	Up to 6000 ¹	Moderna COVID-19 Vaccine	Moderna COVID-19 Vaccine	-	-

Standard of Care ²	Up to 6000	-	-	Moderna COVID-19 Vaccine ³	Moderna COVID-19 Vaccine ³
Observational Group					
Vaccine Declined ⁴	Up to 6000	-	-	-4	-4
Total	Up to 18,000				

1 Immediate Vaccination Group: participants receive Moderna COVID-19 vaccine on enrollment and are given recommendations to follow federal, state, and local guidelines on COVID-19 precautions following vaccination, such as masking, physical distancing, isolation and quarantine.

2 Standard of Care Group: participants are given recommendations to follow federal, state, and local guidelines on COVID-19 vaccination and COVID-19 precautions, such as masking, physical distancing, isolation and quarantine.

3 Vaccine will be offered if participant has not received vaccine outside of the study.

4 Vaccine Declined Group includes participants who prefer not to be vaccinated.

If requested, participant will be offered vaccine if they have not received vaccine outside of the study

2.2 Study Objectives and Endpoints

Primary Objectives	Primary Endpoints
1. To evaluate the efficacy of Moderna COVID-19 Vaccine against SARS-CoV-2 infection (i.e., to evaluate vaccine efficacy against infection or VES).	SARS-CoV-2 infection diagnosed by PCR among participants who were SARS-CoV-2 seronegative at enrollment
2. To evaluate the effect of Moderna COVID-19 Vaccine on peak nasal viral load as a measure of infection and a proxy of infectiousness	Peak viral load in nasal samples from participants diagnosed with SARS-CoV-2 infection among participants who were SARS-CoV-2 seronegative at enrollment
Secondary Objectives	Secondary Endpoints

1. To evaluate the impact of Moderna COVID-19 vaccine on secondary transmission of SARS-CoV-2 infection, using data for the Prospective Close Contact (PCC) cohort and Case-Ascertained Close Contact (CACC) cohort (ie, to evaluate vaccine efficacy against infectiousness or VEI)
	
Number of adjudicated* secondary transmission events in PCC and CACC cohorts from main study participants who were SARS-CoV-2 seronegative at enrollment.
 
*based on questionnaire-based epidemiologic data, antibody and viral dynamics, and viral sequence data

2. To evaluate the efficacy of Moderna COVID-19 Vaccine to prevent serologically confirmed SARS-CoV-2 infection
	
SARS-CoV-2 antibodies to the nucleocapsid protein post visit 3 (month 1), among participants who were SARS-CoV-2 seronegative at enrollment

3. To evaluate vaccine efficacy against COVID-19 disease, (ie, to evaluate VED) using weekly e-diaries and confirmatory PCR testing
	
SARS-CoV-2 infection confirmed by PCR among participants who were SARS-CoV-2 seronegative at enrollment, coincident with the following symptoms:
 
 • at least TWO of the following systemic symptoms: Fever ($\geq 38^{\circ}\text{C}$), chills, myalgia, headache, sore throat, 
OR
 
at least ONE of the following signs/symptoms: cough, shortness of breath or difficulty breathing, new olfactory or taste disorder, clinical or radiographical evidence of pneumonia, thromboembolic event, myocardial infarction, myocarditis, chilblains, or multi-inflammatory syndrome


4. To evaluate vaccine effect on additional measures of magnitude of viral load over time, e.g. area under the viral load curve, duration of shedding, and time to log10 viral load above 10⁵ copies/mL
	
Summary measures of the viral load curve, all evaluated among participants diagnosed with SARS-CoV-2 infection who were SARS-CoV-2 seronegative at enrollment:
 
 • Transmission potential endpoint, defined as 0 for an individual without SARS-CoV-2 infection, and peak log10 viral load, for an individual with SARS-CoV-2 infection • Area under log10 viral load curve (AUC) • Duration of viral shedding (viral load above assay limit of detection) • Area under log10 viral load curve above 10⁵ copies/mL • Duration of viral shedding above 10⁵ copies/mL • Time from enrollment to viral load above 10⁵ copies/mL

5. To evaluate vaccine efficacy against SARS-CoV-2 infection, the vaccine effect on viral load, and the vaccine effect on secondary transmission in all enrolled participants without regard to baseline SARS-CoV-2 serostatus
	
 • SARS-CoV-2 infection diagnosed by PCR [Primary endpoint 1] • Peak log10 viral load in nasal samples from participants who are diagnosed with SARS-CoV-2 infection [Primary endpoint 2] • Number of secondary transmission events in the PCC and CACC [Secondary endpoint 1]

6. To evaluate the immunogenicity of the vaccine
	
Magnitude and response rate of immune responses to vaccination measured at Months 0, and 2 stratified by baseline SARS-CoV-2 serostatus as measured by binding antibody and neutralization assays in the case-cohort immunogenicity set

7. To evaluate immune responses 1 month post-second vaccination as correlates of risk of SARS-CoV-2 acquisition, viral load, secondary infection, and COVID-19 disease among vaccine recipients in the Immediate Vaccination Group
	
Magnitude and response rate of immune responses to vaccination in the Immediate Vaccination Group and measured at Months 0 and 2, stratified by baseline SARS-CoV-2 serostatus, as measured by binding antibody and neutralization assays in the case-cohort immunogenicity set

8. To evaluate vaccine efficacy against asymptomatic SARS-CoV-2 infection
	
SARS-CoV-2 infection by PCR or periodic serology among participants seronegative for SARS-CoV-2 at baseline and without any prior reporting of symptoms that led to confirmation of a COVID-19 disease endpoint


9. To evaluate vaccine efficacy against SARS-CoV-2 infection and COVID-19 disease and the vaccine effect on viral load and secondary transmission among participants who received all planned immunizations at the designated immunization visits within specific visit windows
	
Endpoints evaluated among participants who were SARS-CoV-2 seronegative at enrollment
 
 • SARS-CoV-2 infection diagnosed by PCR [Primary endpoint 1] • Peak log₁₀ viral load in nasal samples from participants who are diagnosed with SARS-CoV-2 infection [Primary endpoint 2] • Number of secondary transmission events in the PCC and CACC [Secondary endpoint 1] • SARS-CoV-2 infection coincident with signs and symptoms of COVID-19 listed under Secondary endpoint 3

10. To evaluate the association between measures of the magnitude of viral load over time and secondary transmission of SARS-CoV-2 infection, among individuals with incident SARS-CoV-2 infection in each treatment group, i.e. to conduct analyses aimed at evaluating viral load measures as surrogates of secondary transmission
	
 • Peak log₁₀ viral load [Primary endpoint 2] and other viral load summaries [Secondary endpoints 4] • Number of secondary transmission events in the PCC cohort and CACC cohort [Secondary endpoint 1]

11. To evaluate vaccine effects on peak viral load and on secondary transmission of SARS-CoV-2 infection separately among individuals with asymptomatic vs. symptomatic SARS-CoV-2 infection
	
 • Peak log₁₀ viral load [Primary endpoint 2] and other viral load summaries [Secondary endpoints 4] • Number of secondary transmission events in the PCC cohort and CACC cohort [Secondary endpoint 1] • SARS-CoV-2 infection diagnosed using PCR, with and without signs and symptoms of COVID-19 listed under Secondary endpoint 3

Exploratory Objectives
	

1. To evaluate the associations between demographic and clinical factors and secondary transmission of SARS-CoV-2 infection and COVID-19 disease, among individuals with incident SARS-CoV-2 infection in the main study cohort and their contacts in the PCC and CACC
2. To assess if and how vaccine efficacy against SARS-CoV-2 infection, transmission and COVID-19 disease depends on baseline demographic, clinical, socio-economic indicators, and/or behavioral characteristics of study participants
3. To assess if and how vaccine efficacy against SARS-CoV-2 infection and COVID-19 disease depends on genotypic or neutralization phenotypic characteristics of SARS-CoV-2 (sieve analysis)

2.3 Randomization

14,400 participant slots (20% more than the planned 12,000 participants) were randomized into the Immediate and SoC groups with the 1:1 allocation ratio, stratification by site and place of residence (Dormitory or campus housing, Fraternity or sorority house, Apartment building or condo, Stand-alone house (non-fraternity or sorority, Shelter, RV / Trailer, Staying with friends / Couch surfing, No residence and Other) and 1:1:1 mix of block sizes 8, 10 and 12 created in a random order. Released randomized participants could not be re-randomized into the study (but were allowed to enroll in the Vaccine Declined group). The released randomization slots were not re-used by other (replacement) participants.

2.5 Sample Size and Power

At the design stage, sample size calculations assumed 48,000 person-months of follow-up (even between vaccinated and unvaccinated, with the latter potentially including the Vaccine Declined group), 5% loss-to-follow-up rate, 10% baseline sero-positivity, 98% per-protocol rate, SARS-CoV-2 infection endpoint post Day 29 among baseline seronegative participants in the D29- set with 4% event incidence over 16 weeks (constant over time) among unvaccinated. Under these assumptions, the study had 90% power to detect $VE > 57\%$ using one-sided 0.025-level log-rank test. Additionally, assuming 50% VE we expected (50% probability) at least 225 post-Day 29 events to be available to estimate the vaccine effect on mean peak log10 viral load. The assumed 225 events, SD in peak log10 viral load = 1.8 (equal in both arms), 1-sided 0.025-level two-sample t-test yielded 96.9% power.

Due to early termination of the trial, the study is underpowered to address primary study objectives.

3. GENERAL DATA ANALYSIS CONSIDERATIONS

3.1 Analysis Set(s)

Full Analysis Set (FAS): Limited analyses (e.g. participant characteristics at the baseline) will be carried out among all main study participants that satisfy inclusion criteria and enroll in the study.

Full Analysis Set with PCR data (FAS-P): Only FAS participants with study PCR data will contribute acquisition and viral load (ΔVL) endpoint data and will be used as a main study secondary data set to estimate endpoint parameters. FAS-P participants will be further limited to participants enrolled as randomized to estimate vaccine efficacy against infection (VES). This set will be considered a main study secondary data set.

Baseline SARS-CoV-2 negative set (Main study primary data set): To account for ramping vaccine efficacy (VE), the protocol stipulated that primary analyses would be conducted among all baseline SARS-CoV-2 negative participants, and again among participants in the “Day 29 Negative Set”—the set of participants without seroconversion or PCR-confirmed infection on or prior to second vaccination on Day 29. The intent of this plan was to evaluate effects of the full two-dose vaccine regimen. Given that time of second vaccination is not easily defined in the SoC and Vaccine Declined groups and given that some participants in the Immediate Vaccination group began swabbing and accruing person-time and infection events before first vaccination, primary analyses will instead be conducted among all eligible enrolled baseline SARS-CoV-2 negative participants (Baseline SARS-CoV-2 negative set). All person-time and events will be included, and ramping VE will be accommodated using analyses that estimate vaccine effects according to number of doses received. Baseline SARS-CoV-2 negativity will be defined as PCR negative based on the first resulted (see section 3.2.9 for exclusions) nasal swab and seronegative based on the first qualifying (see section 3.2.8 for exclusions) blood sample closest to the first resulted swab. Note that blood collection for determining baseline serostatus was intended to occur coincident with initiation of swabbing; however, some participants had blood collected well before they began swabbing, and others had blood collected well after the initiation of swabbing. The analysis will summarize the distribution of time between first resulted swab and first blood. Qualifying blood sample closest to the first resulted swab date will be defined as either the closest qualifying blood sample on or before the first resulted swab date (if it exists) or the closest qualifying blood sample after the first resulted swab date (if no qualifying blood sample exists on or before the first resulted swab date). Primary analyses of vaccine efficacy against infection (VES) and of the vaccine effect on viral load (ΔVL) will be conducted among Baseline SARS-CoV-2 negative set participants that were enrolled as randomized.

All primary and secondary analyses will be done according to enrollment group, ie, Immediate Vaccination Group, Standard of Care Group, or Vaccine Declined Group.

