Appendix E Procedures for Main Cohort, Immediate Vaccination Group

Visit:	01 ¹	02 ²	03	04	05	06
Day:		D1	D29	D57	D113	D141
Week:		W0	W4	W8	W16	W20
Month:		M0	M1	M2	M4	M5
Procedure	Scr.	VAC1	VAC2			
Study procedures						
Screening consent (if used)	✓	—	—	—	—	—
Assessment of understanding	✓	—	—	—	—	—
Protocol consent (eConsent)	✓	—	—	—	—	—
Medical history questionnaire ³	✓	✓	—	—	—	—
SARS-CoV-2 infection risk assessment ³	✓		Weekly			
COVID-19 symptom surveillance ³	—		Weekly starts at week 2, not during week 5			
Confirm eligibility	✓	—	—	—	—	—
Obtain demographics ³	✓	—	—	—	—	—
Randomize	—	✓	—	—	—	—
SARS-CoV-2 testing questionnaire ³	—		approximately 2x per week			
End of study questionnaire ³	—	—	—	—	✓	—
Research Samples⁴						
Serum for Immunogenicity Assays and Storage	—	✓	—	✓	—	—
Serum for SARS-CoV-2 clinical serology ⁵	—	✓ ⁶	—	✓ ⁶	✓	—
Nasal swab	—		Daily ⁷			
Vaccination procedures						
COVID-19 symptom check ⁸	—	✓	✓	—	—	—
Vaccination	—	✓	✓	—	—	—

Greyed out visit column does not apply to this group.

1 Screening may occur over the course of several contacts/visits up to and including day 1, prior to vaccination.

2 Blood draws required at vaccination visits must be performed prior to vaccination.

3 Results from screening at school, if applicable, or at other locations will be captured via eDiary, please see Section 9.16.

4 From screening to the final study visit, the total blood volume to be collected from each participant will be approximately 40 mL (maximum) with a maximum of approximately 17 mL collected in a single visit.

5 For blood self-collected by a participant the maximum volume will be less than 1 mL in a single collection.

6 SARS-CoV-2 clinical serology testing may be performed on leftover blood from samples collected for immunogenicity assays. No separate blood sample is needed. If a Main cohort participant is also in the Prospective Close Contact (PCC) cohort related to

an index case or in the Case-ascertained Close Contact (CACC) cohort, one additional blood collection (self-collection) will be performed (see table below).

7 Daily swabs will be collected from vaccination through D113. Swabs will be returned via drop-off location(s) specified by the clinic or through the mail.

8 COVID-19 Symptom Check to be performed within 24 hours prior to vaccination.

The following **additional** procedures will occur for Main cohort, immediate vaccination participants, who fall under any of the following categories:

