3.2 Statistical Analysis Issues

3.2.1 Time scales

The analysis will utilize two different time scales. “Calendar time” will be defined as time since enrollment of the first study participant. “Study time” will be defined as time from either the first

nasal swab (if the first swab result was negative) or 90 days after the first swab (if first swab positive). Note that while randomization would be the ideal origin for study time, some participants did not begin swabbing until days or even weeks into the study, and infection status and timing of infection cannot be determined prior to the initiation of swabbing.

3.2.2 *Incident infection*

An incident SARS-CoV-2 infection will be defined as the first instance of a positive PCR result that follows at least one negative PCR result. Therefore, for participants who are baseline SARS-CoV-2 positive (i.e. seropositive at first blood collection or PCR positive on first swab), an incident infection occurs only 90 days after the first swab and once there is at least one negative PCR followed by a positive PCR.

3.2.3 *Seroconversion*

A seroconversion event will be defined as the first instance of a positive serology result that follows at least one negative serology result.

3.2.4 *Censoring approaches*

The following analyses will use the following censoring approaches (as specified in analytical approach). For the primary endpoint, “test” refers to a PCR test of a nasal swab. For the secondary endpoint of seroconversion, “test” refers to serology of a blood sample.

- ITT censoring: In the SoC arm, follow-up time is censored at the last negative test prior to end of study vaccination or the last negative test if the participant is not vaccinated on study (both are ignored if the first positive test occurs after the last negative test). In the Immediate Vaccination arm and the Vaccine Declined group, follow-up will be censored at the last negative test (ignored if the first positive test occurs after the last negative test). The timing of any test is considered to be the day on which the assay was collected, where day is defined from 3AM to 3AM of local time of the site.

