Alluvial plots will be used to explore noncompliance over study and calendar time, by enrollment group and study site and other baseline covariates. Descriptive tables will summarize noncompliance over study time by enrollment group. Compliance will be defined in two ways, with swabs expected starting from either 1. enrollment date or 2. first swab date (or enrollment date if participant had no swabs). Days with a swab will be expected until minimum of the day before the date CRF-confirmed study completion, 111 days after enrollment and the last expected swabbing date (Dec. 31, 2021). Additionally, swabs will not be expected after outside vaccination

or termination. Time (weeks) after these two events (outside vaccination and termination) will be displayed separately in the plots. Compliance metric for participant weeks with at least one expected swab day will be the % (of expected) days with a swab, categorized as 0%, 1-29%, 30-58% and 59-100% (these categories will be labelled as 0, 1-2, 3-4 and 5-7, respectively, corresponding to a week with 7 expected swab days).

A GEE model will be used to explore predictors of time-varying non-compliance. Baseline and time-varying covariates listed in 3.2.5 will be considered for inclusion in the model. Participants will be censored at the earliest of outside vaccination or study termination.

If predictors of non-compliance, other than enrollment group, study time, calendar time, and covariates associated with outside vaccination (Section 3.2.5) or exposure risk (Section 3.2.6) are identified, these will be accounted for in efficacy analyses described in Section 7 through covariate adjustment or IPCW.

3.2.8 *Blood sample exclusions*

Prior to deriving the baseline serostatus and the seroconversion event, the following blood sample data will be excluded to account for replacements or problematic samples:

- Original insufficient in-clinic samples when replacement samples were collected for the same visit (see Section 8 of the Phlebotomy Specimen Collection Study Specific Procedures)
- Self-collected (TASSO) samples resulted as “Test Not Performed” by the lab (due to various reasons, e.g. insufficient/incorrect/damaged/expired/unused sample, processing error)
- In-clinic samples with more than 90 days between blood draw and lab processing
- TASSO samples with more than 7 days between blood draw and lab receipt

3.2.9 *Nasal swab record exclusions*

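### With no time limit on the baseline blood, a late sample can turn an on-study infection into a baseline exclusion, so membership of the primary set depends on the outcome

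*SAP*

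**What the plan says.** SAP 3.1 (Baseline SARS-CoV-2 negative set) requires a PCR-negative first resulted swab and a seronegative result on the qualifying "blood sample closest to the first resulted swab". A sample on or before the swab takes precedence. Failing that, the sample is "the closest qualifying blood sample after the first resulted swab date". No maximum interval is given.

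The same paragraph records that blood was meant to coincide with the start of swabbing, but that "others had blood collected well after the initiation of swabbing". The only handling planned there is descriptive: "The analysis will summarize the distribution of time between first resulted swab and first blood".

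SAP 3.2.8 removes some samples before baseline serostatus is derived, for example "TASSO samples with more than 7 days between blood draw and lab receipt". Its time limits run from draw to laboratory, not from swab to draw, so an exclusion can move the first qualifying sample later. Protocol 6.4.3.2 schedules serology at Months 0, 2 and 4.

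SAP 3.2.1 and 7.1 start incident follow-up at the first swab when that swab is negative. SAP 7.2 restricts the primary analysis to baseline-negative participants enrolled as randomized.

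**The concern.** Time at risk begins at the first negative swab, but entry to the primary set can rest on a serology result obtained weeks later. Infection during that interval can change the result. The participant who was infected and seroconverted leaves the set together with the event. The participant who was not infected stays, with all of the person-time. That is selection on the outcome, and it conflicts with the SAP 3.1 statement that all person-time and events are included.

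Two things are at stake. Primary endpoint events are lost from an analysis that SAP 2.5 already calls underpowered. VE may also be biased if late draws, or the chance of seroconverting before them, differ between arms.

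**Working it through.** **1. The rule applied to one participant (invented dates).** First swab negative on day 1; no qualifying Month 0 blood; study PCR positive on day 20; first qualifying blood at Month 2 (day 57), seropositive.
- SAP 3.1: the day-57 sample is the closest after the swab, so the participant is not baseline negative.
- SAP 5.1 disposition table: counted as baseline seropositive.
- SAP 7.2: outside the primary set, so the day-20 infection is not counted.
- The same participant with no infection and a seronegative day-57 sample is kept from day 1.

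**2. Does a supportive analysis restore the event?** SAP 7.2.1 plans an analysis that includes baseline positives. SAP 3.2.2 says that anyone seropositive at first blood, or PCR positive on the first swab, can have an incident infection only from 90 days after the first swab; the day-20 event would not count. SAP 3.2.1 and 7.1 apply the 90-day delay only when the first swab was positive; the day-20 event would count. The two rules give different answers.

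**3. Check of the event model.** The plan gives no figure for this issue, so I first tested the infection and loss model on the design figure of 225 post-Day 29 events (Protocol 6.1; inputs from Table 6-2). Weekly infection rate l = −ln(0.96)/16, halved for the vaccinated; loss rate m = −ln(0.95)/16; n = 6,000 × 0.90 × 0.98 = 5,292 per group.

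Events = n · l/(l+m) · [exp(−4(l+m)) − exp(−16(l+m))] = 153.0 + 77.5 = 230.5, or 2.4% above 225. That is close enough for illustration.

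**4. Assumptions not in the documents.** The share of late draws; their timing; a 14-day lag from infection to seropositivity; a seroconversion probability s of 0.6 to 1.0. The low end uses the figure in Protocol 2.4 that 40% of asymptomatic infections were IgG negative at 8 weeks. Applied to all infections, it is a lower bound.

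**5. Balanced late draws.** n = 6,000 × 0.90 = 5,400 per arm; 16 weeks; no efficacy for the first 2 weeks, then 50%. Expected infections: 120 Immediate, 211 SoC; crude rate-ratio VE over all follow-up 0.435. With 20% of each arm judged on its late sample:

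| Blood drawn | s | Removed, Immediate / SoC | Share of all events | VE |
|---|---|---|---|---|
| Week 4 | 1.0 | 5.5 / 5.5 | 3.3% | 0.447 |
| Week 8 | 0.6 | 6.5 / 9.8 | 4.9% | 0.440 |
| Week 8 | 1.0 | 10.9 / 16.3 | 8.2% | 0.444 |
| Week 16 | 1.0 | 21.4 / 37.1 | 17.7% | 0.438 |

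Across shares of 10–20%, 1–18% of events are lost and VE is at most 0.447. The small shift is upward.

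**6. Late draws in SoC only.** Take a constant true VE of 50%, constant incidence over 112 days, and 20% of SoC judged on day 57. The fraction of SoC events removed is f = 0.20 × (57 − 14)/112 × s, and the apparent VE is 1 − 0.50/(1 − f).
- s = 1.0: f = 7.7%; VE = 1 − 0.50/0.923 = 45.8%.
- s = 0.6: f = 4.6%; VE = 1 − 0.50/0.954 = 47.6%.
- A milder case, 10% of SoC on day 29 with s = 1.0: f = 0.10 × 15/112 = 1.3%; VE = 49.3%.

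These are crude ratios. The SAP model is a calendar-time Cox model stratified by site with dose-specific terms, which I did not simulate.

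**The case against.** The strongest reply is that the late sample is only a fallback, that the SAP discloses the timing problem and will tabulate the gap, and that nothing shows the arms differ. Most of that stands. The problem touches only participants with no qualifying blood by the first swab, and their number is not given. Nor is all of their early person-time protected: infections shortly before the draw, and those that never seroconvert, still count.

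A reader might infer that late bloods sit mainly in SoC, so that VE is biased downward. The support would be Protocol Appendix E for the Immediate arm: "Blood draws required at vaccination visits must be performed prior to vaccination". SoC has no dose to anchor its Day 1 draw. The inference is plausible but not documented. SAP 3.1 says some Immediate participants began swabbing before their first dose, so blood before dose 1 need not mean blood before the first swab. Both arms have a Day 1 sample and the same guideline of about 7 working days to complete Visit 2 (Protocol 9.3 and 9.5). The SAP 3.2.8 exclusions are not arm-specific. No count by arm appears anywhere.

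It can also be said that SAP 2.4 treats the randomized analyses as post hoc, and that a shift of a few points is small beside their imprecision. That limits the consequence but does not justify the rule. A gap summary shows how often the rule could bite; it does not put any event back.

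**Conclusion.** The flaw is real. The baseline definition has no time limit, follow-up starts before the late draw, and an on-study infection can remove its own participant from the primary set. Neither the gap summary nor the analysis that adds baseline positives clearly repairs this, because the 90-day rule is stated in two incompatible ways.

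The effect on VE is conditional. With balanced late draws and seroconversion, VE barely changes and the cost is lost events, 1–18% in the scenarios shown. If late draws are commoner in SoC, VE is biased downward: from 50% to about 46–48% with 20% of SoC judged at day 57, less with earlier or fewer late draws, more with later or more frequent ones. The late-draw shares, the 14-day lag and the seroconversion range are assumptions, so these figures illustrate the mechanism and do not estimate its size in this trial. A firm claim of downward bias would go beyond the documents.

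**What to change.** 1. In SAP 3.1, accept a blood drawn after the first resulted swab as baseline only within a short stated window, for example 14 days. That is too short for most on-study infections to seroconvert; under the 14-day lag assumed above, none would be removed.
2. For participants with no qualifying blood by the end of the window, apply one rule that ignores the later result. Excluding them from the primary set is preferable, because it keeps the seronegative population that the protocol defines. Add a sensitivity analysis that keeps them on first-swab PCR status.
3. Do not instead rescue only those whose late seropositive result follows a positive study PCR. That would keep people because they became cases and drop seropositive non-cases from the same interval, which again selects on outcome.
4. Report, by arm, how many participants had their first qualifying blood after the first swab, and the delay.
5. Reconcile SAP 3.2.2 with 3.2.1 and 7.1, so that the analysis including baseline positives has one event rule.

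The cost is SAP wording, a change to the set derivation and one more sensitivity run. Some participants are lost from the primary set; item 4 shows how many.
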